ARDS	Acute Respiratory Distress Syndrome
CE	Cost-Effective
DSMB	Data Safety Monitoring Board
ICU	Intensive Care Unit
LOS	Length Of Stay
METC	Medical Research Ethical Committee (MREC) in Dutch: Medische Ethische Toetsings Commissie
NAS	Nurse & Activity Score
PBW	Predicted Body Weight
PEEP	Positive End-Expiratory Pressure
RCT	Randomized Controlled Trial
SAE	Serious Adverse Event
Sponsor	The party that commissions the organization or performance of the research, for example a pharmaceutical company, academic hospital, scientific organization or investigator; a party that provides funding for a study but does not commission is not regarded as the sponsor, but referred to as a subsidizing party
TISS	Therapeutic Intervention Scoring System
VFD-28	Ventilator-Free Days and alive at day 28

SUMMARY

Rationale: While there is sufficient randomized controlled trial—evidence for benefit of higher levels of positive end-expiratory pressure (PEEP) during ventilation of intensive care unit (ICU) patients with acute respiratory distress syndrome (ARDS), evidence for benefit of PEEP, at any level, during ventilation of ICU patients without ARDS is still insufficient. One recent metaanalysis suggests no benefit of PEEP in ICU patients without ARDS. Nevertheless, there is a trend to use higher PEEP levels in these patients in recent years.

Hypothesis: We hypothesize that ventilation with the lowest possible PEEP level ('restricted PEEP', i.e., the lowest PEEP level resulting in an acceptable level of oxygenation) is as effective and safe as ventilation with the PEEP level currently practiced ('liberal PEEP', i.e., a PEEP level of 8 cm H₂O, the median PEEP level applied in these patients in the Netherlands) in ICU patients without ARDS.

Objective: To compare ventilation with the lowest possible PEEP level to ventilation with the PEEP level currently practiced in ICU patients without ARDS.

Study design: National multicenter, non-inferiority, open, randomized controlled trial in intubated and ventilated adult ICU patients without ARDS.

Study population: Consecutive intubated and ventilated adult ICU patients without ARDS with an anticipated duration of ventilation of at least 24 hours.

Procedure: Patients are randomly assigned in a 1:1 ratio to the 'restricted PEEP'—arm or to the 'liberal PEEP'—arm of this trial.

Study endpoints: The primary endpoint is the number of ventilator-free days and alive at day 28. Secondary endpoints include ICU- and hospital length of stay (LOS), ICU- and hospital, and 90-day mortality, incidence of severe hypoxemia, severe atelectasis and the need for rescue therapies, pneumonia, pneumothorax, the incidence and development of ARDS and days with use of hemodynamic support and with use of sedation. Also, therapeutic intervention scoring system (TISS)/ Nursing Activities Score (NAS) and related healthcare costs will be estimated and compared.

Nature and extent of the burden and risks associated with participation, benefit and group relatedness: Differences in burden and risk of the two ventilation

strategies are uncertain. Ventilation with the lowest possible PEEP level could increase the risk of atelectasis and also the risk of potentially dangerous hypoxemia, which can be adequately treated within the ICU setting. Ventilation with the PEEP level currently practiced could increase the amount of overdistended lung tissue and increase

hemodynamic compromise. No other study interventions are performed. Collection of demographic data, ventilation data and outcome data causes no harm for the patients.

1. INTRODUCTION AND RATIONALE

1.1 Mechanical ventilation associated lung injury

Mechanical ventilation is typically seen as a life-saving intervention in critically ill patients, despite increasing and unequivocal evidence that it can aggravate and even initiate lung injury.¹ Indeed, ventilation may contribute to development of atelectasis,^{2,3} increasing the risk of repetitive opening and closing of lung tissue, a phenomenon frequently referred to as 'atelectrauma'.¹ Results from preclinical studies using animals^{4,5} and studies in humans^{6,7} support the use of positive end-expiratory pressure (PEEP) during ventilation to prevent, or at least minimize the risk of atelectrauma. Ventilation with PEEP, however, can also lead to lung injury due to overdistension,^{8,9} frequently referred to as 'volutrauma'.¹

1.2 Pulmonary effects of PEEP

Atelectasis is more extensive in patients with the acute respiratory distress syndrome (ARDS) than in patients without lung injury, and are more frequently seen with mandatory than spontaneous forms of ventilation.^{10,11} In patients with ARDS, seen the balance between the positive effects of higher PEEP levels (i.e., reduction in atelectrauma, by reducing atelectasis) and negative effects of higher PEEP levels (i.e., increase in volutrauma, by increasing overdistension), ventilation with a higher PEEP level could result in a net beneficial effect. In patients without ARDS, however, patients who also more frequently receive spontaneous forms of ventilation, the balance between benefit and harm could go into the other direction, as the reduction in atelectrauma could be minimal or negligible, at a price of more volutrauma.

The results of one metaanalysis using the individual patient data from three large randomized controlled trials (RCTs) comparing higher to lower PEEP levels during ventilation of patients with ARDS suggests benefit of higher PEEP levels (albeit only in patients with more severe form of ARDS).¹²⁻¹⁵ Sufficiently large RCTs comparing higher to lower PEEP levels during ventilation of patients without ARDS are presently lacking, and the available data does not allow individual patient data metaanalyses.¹⁶

1.3 Non-pulmonary effects of PEEP

Besides increasing lung aeration, ventilation with PEEP could also have extrapulmonary effects. Ventilation with PEEP affects the loading conditions of the heart,¹⁷ as every increase in intrathoracic pressure reduces the preload of the heart

and might increase as well as decrease the afterload of the right ventricle depending on whether lung tissue is recruited by PEEP.¹⁷ The effects of ventilation with PEEP on cardiac performance could also differ between patients with ARDS and patients without lung injury. Ventilation with higher PEEP levels could reduce right ventricle afterload through the prevention of atelectases in ARDS patients, while it could increase right ventricle afterload and reduce left ventricle preload through increases in overdistended lung tissue in patients without ARDS. RCTs evaluating the extrapulmonary effects of PEEP are lacking, both in ventilated patients with ARDS, and ventilated patients without ARDS.

1.4 Systematic review and metaanalysis of RCTs of PEEP

A recent systematic review and metaanalysis of RCTs in patients without ARDS did not find benefit from ventilation with higher PEEP levels with regard to mortality and duration of ventilation, neither in surgical ICU patients nor in medical ICU patients.¹⁶ The analysis even suggested no benefit of any level of PEEP in these patients. There were no differences found in the incidence of hypotension and blood pressure levels between ventilation with higher PEEP levels versus lower PEEP levels.

1.5 Is there benefit of intraoperative PEEP?

The effects of PEEP during ventilation gained also interest from anesthesiologists, who struggle with the same question of whether or not to use PEEP in surgery patients without lung injury. Three RCTs showed that ventilation with PEEP combined with low tidal volumes was associated with better outcomes compared to ventilation without or a low level of PEEP combined with high tidal volumes.¹⁸⁻²⁰ These RCTs thus studied the effect of a bundle of ventilator settings that are both expected to have an effect on the lungs, and it is impossible to conclude which part of the bundle was responsible for the benefit found. A more recent RCT, however, showed no difference in the incidence of pulmonary complication when no PEEP was compared to PEEP during ventilation at low tidal volumes.²¹ Furthermore, one individual patient metaanalysis using data from all four RCTs mentioned above suggests that benefit seemed to come mainly from restrictions in tidal volume size, and not from using higher levels of PEEP, in patients undergoing intraoperative ventilation during general anesthesia for surgery.²²

1.6 An historical perspective

In the early years of mechanical ventilation, PEEP was seldom used because of its alleged negative effects on hemodynamics.²³ Most RCTs of PEEP in ICU patients

without ARDS compared ventilation with some level of PEEP to no PEEP (figure 1). In the 1960s, Ashbaugh observed that PEEP improved oxygenation in mechanically ventilated patients with ARDS, triggering the use of PEEP in patients with this life-threatening complication of critical illness.²⁴ In the 1970s, animal experiments suggested that prophylactic PEEP could be beneficial as well,²⁵⁻²⁷ maybe even preventing development of ARDS.^{28,29} Since then PEEP is increasingly used, also in patients without ARDS, despite evidence for benefit of this strategy.

[figure not shown]

Figure 1. PEEP levels in randomized controlled trials in patients without ARDS.¹⁶

1.7 Current PEEP practice in ICU patients without ARDS

Due to absence of RCT-evidence, it is highly uncertain what the best PEEP level is in ICU patients without ARDS. Interestingly, there is a salient tendency to use higher PEEP levels in these patients.³⁰⁻³² Even more surprising, in the Netherlands ICU patients without ARDS are ventilated with a median PEEP level of 8 cm H₂O, higher compared to a PEEP level of 6 cm H₂O in surrounding countries,³³ and what is reported to be used worldwide.³⁴

1.8 Need for a new RCT of PEEP in patients without ARDS

While guidelines recommend using higher PEEP levels in ICU patients with ARDS, recommendations regarding the PEEP level to use in ICU patients without lung injury

are lacking. Often a minimum PEEP level of 5 cm H₂O is recommended, though this is without any scientific support. Consequently, the ICU community requests a well-powered high-quality RCT comparing ventilation with higher versus lower PEEP levels in ICU patients without ARDS.¹⁶ This RCT should use objective and patient-relevant outcomes, such as duration of ventilation and ICU- and hospital length of stay (LOS), amongst others.

1.9 The RELAx trial

The 'REstricted versus Liberal positive end-expiratory pressure in patients without Acute respiratory distress syndrome' (RELAx) trial is a national multicenter open randomized controlled trial in ICU patients without ARDS at start of ventilation. It will be the first RCT comparing ventilation with the lowest possible PEEP level with ventilation with the median PEEP level currently practiced in the Netherlands that recruits a sufficient number of patients to test the hypothesis that ventilation with the lowest possible PEEP level is non-inferior to ventilation with a PEEP level of 8 cm H₂O with regard to objective and patient-relevant clinical endpoints.

2. OBJECTIVES AND HYPOTHESIS

2.1 Objectives

2.1.1 Primary objective

The aim of the RELAX trial is to compare ventilation with the lowest possible PEEP level ('restricted PEEP', i.e., the lowest PEEP level resulting in an acceptable level of oxygenation) to ventilation with the PEEP level currently practiced ('liberal PEEP', i.e., a PEEP level of 8 cm H₂O, the median PEEP level in these patients in the Netherlands) in intubated and ventilated ICU patients not fulfilling the consensus definition for ARDS at start of ventilation.

2.1.2. Secondary objectives

Secondary objectives are to compare the effects of '*restricted PEEP*' vs. '*liberal PEEP*' on ICU- and hospital length of stay (LOS), ICU- and hospital, and 90-day mortality, the incidence of severe hypoxemia, severe atelectasis, and the need for rescue therapies including recruitment maneuvers, bronchoscopy and prone position, pneumonia, pneumothorax, the incidence and development of ARDS, days with use of hemodynamic support and with use of sedation, therapeutic intervention scoring system (TISS)/ Nursing Activities Score (NAS) and related healthcare costs.

2.2 Hypothesis

2.2.1 Primary hypothesis

We hypothesize that ventilation with the lowest possible PEEP level results in a similar number of ventilator-free days at day 28 as ventilation with the PEEP level currently practiced in ICU patients without ARDS.

2.2.2. Secondary hypotheses

The secondary hypotheses are that ventilation with the lowest possible PEEP level is equal to ventilation with the PEEP level currently practiced in ICU patients without ARDS, with regard to the other endpoints mentioned above.

3. STUDY DESIGN

The RELAX trial is a national multicenter, non-inferiority, open, randomized controlled trial in intubated and ventilated adult ICU patients without ARDS expected to need ventilation for at least 24 hours. A total of 980 ICU patients in 12 participating academic as well as non-academic centers will be included.

4. STUDY POPULATION

4.1 Population

The RELAX trial will recruit consecutive intubated and mechanically ventilated ICU patients without ARDS at onset of ventilation and who are expected to need ventilation > 24 hours. Patients are included in the ICUs of 3 academic and 9 non-academic centers in the Netherlands. Patients are screened for eligibility and randomized within one hour after initiation of invasive ventilation or, if already intubated and ventilated before admission, on ICU admission. A total of 980 patients will be randomized; approximately 82 patients per center.

4.2 Inclusion criteria

In order to be eligible to participate in this trial, patients must meet all of the following criteria:

- Admission to one of the participating ICUs
- Need for and start of invasive ventilation
- An expected duration of ventilation > 24 hours

4.3 Exclusion criteria

Patients who meet any of the following criteria will be excluded:

- Age less than 18 years
- Patients with a clinical diagnosis of ARDS or possible ARDS with a $\text{PaO}_2/\text{FiO}_2 < 200 \text{ mmHg}$ (as the benefit of ventilation with higher PEEP levels has been proven in these patients; see **text box 1**)
- Patients with ongoing cardiac ischemia due to cardiac infarction and failed revascularization, patients with increased and uncontrollable intracranial pressure (of $\geq 18 \text{ mmHg}$), patients with delayed cerebral ischemia after subarachnoid hemorrhage, patients with necrotizing fasciitis, and severe untreatable anemia such as in case of Jehovah's Witnesses (as these patients can be considered to be vulnerable to the potentially dangerous hypoxemia which could develop more often, even for a short time, in the 'restricted PEEP'-arm of this trial; see **text box 2**)
- Patients previously randomized in this RCT
- Patients participating in another RCT with the same clinical endpoint, or interventions possibly compromising the primary outcome

- Invasive ventilation longer than 12 hours directly preceding the present ICU admission
- Invasive ventilation longer than 1 hour before randomization
- Patients with suspected or confirmed pregnancy
- Patients with morbid obesity (body mass index > 40)
- Patients with GOLD classification III or IV chronic obstructive pulmonary disease (COPD)
- Patients with premorbid restrictive pulmonary disease (evidence of chronic interstitial infiltration on chest radiographs)
- Patients in whom pulse oximetry is known to be unreliable, e.g., patients with carbon monoxide poisoning
- Any neurologic diagnosis that can prolong duration of mechanical ventilation, e.g., patients with Guillain–Barré syndrome, high spinal cord lesion or amyotrophic lateral sclerosis, multiple sclerosis, or myasthenia gravis
- Patients receiving veno-venous, veno-arterial or arterio-venous extracorporeal membrane oxygenation (ECMO)
- No informed consent

Text Box 1 – Diagnosing ARDS

The diagnosis of ARDS is clinical, requiring (a) a medical history, (b) the presence of bilateral opacities on the chest radiograph that are fully explained by effusions, lobar/lung collapse or nodules, and (c) respiratory failure not fully explained by cardiac failure or fluid overload. The $\text{PaO}_2/\text{FiO}_2$ is used to classify ARDS severity, with a $\text{PaO}_2/\text{FiO}_2$ between 200 and 300 mmHg indicating mild ARDS, and a $\text{PaO}_2/\text{FiO}_2 < 200$ mm Hg indicating moderate or severe ARDS.

The diagnostic approach, however, could be difficult if not impossible in ICU patients within the first hour after intubation and start of ventilation: they frequently suffer from temporary post-intubation atelectasis as a reason for a low $\text{PaO}_2/\text{FiO}_2$, the medical history is often not yet complete, and imaging studies are usually not yet performed or the results available. The risk is that only the $\text{PaO}_2/\text{FiO}_2$ is used to diagnose ARDS in the short time frame after intubation, which could induce severe bias, as many of these patients do not have ARDS.

Thus, we exclude all patients that are clinically diagnosed with ARDS. **Patients with a $\text{PaO}_2/\text{FiO}_2 < 200$ mm Hg are also excluded** since we consider these patients at high risk of having ARDS; only when the attending physician explicitly states the patients has no ARDS *and* no direct risk factor for ARDS is present, the patient can be included. Patients without ARDS and with a $\text{PaO}_2/\text{FiO}_2$ between 200 and 300 mmHg can be included: as these patients very seldom have ARDS.

Text Box 2 – Potentially vulnerable patients

Oxygen delivery to the tissues (DO_2) depends on cardiac output and arterial blood oxygen content,³⁵ the latter being dependent on hemoglobin saturation, arterial blood oxygen saturation (SaO_2) and partial pressure of oxygen (PaO_2). The understanding of the importance of the several components of DO_2 has led to emphasize early identification and prevention of hypovolemia (to prevent a low cardiac output) and anemia, but also prevention of hypoxemia for critically ill patients.

Administration of fluids, packed red blood cells, and additional oxygen could all be useful, though the effect size on DO_2 differs substantially. Indeed, a 50%–decrease in hemoglobin concentration (e.g., from 9 to 4.5 mmol/l) results in a 50% reduction of DO_2 , whereas a 50%–reduction in the PaO_2 (e.g., from 12 to 6 kPa, or SaO_2 (from 98 to 78%) results only in no more than 20% decrease in DO_2 . Thus, the influence of a drop in hemoglobin concentration is of greater influence on DO_2 as compared to a drop in PaO_2 or SaO_2 .

Nevertheless, the targeted O_2 saturation proposed in this RCT could potentially be harmful in certain patient groups, like those with proven ongoing cardiac ischemia or delayed cerebral ischemia, or necrotizing fasciitis, or severe untreatable anemia such as in case of Jehovah's Witnesses. Therefore, these patients should be excluded from participation in this trial.

4.4 Sample size

Group size calculation is focused on demonstrating non–inferiority. When the sample size in each is 445, an one–sided non–inferiority t–test (targeted at 0.05 significance level) for the difference in means of log–transformed normalized data has a 80% power to reject the null hypothesis that the number of VFD–28 in the 'restricted PEEP'–arm is inferior to the number of VFD–28 in the 'liberal PEEP'–arm by a margin of 10% anticipating on a coefficient of a variation of 0.70 (www.stichting-nice.nl), in favor of the alternative hypothesis that the number of VFD–28 in the 'restricted PEEP'–arm is non–inferior.

The choice for a margin of 10% is motivated by what we consider acceptable from a clinical point of view as the maximal acceptable reduction of the ventilator–free period for non–inferiority. Clinically this margin means that an increase of > 10% in the

duration of mechanical ventilation will reduce the VFD-28 with > 12 hours (calculated over the expected mean duration of mechanical ventilation of 5 days) (<http://www.stichting-nice.nl>) which will be considered inferior. To allow for an anticipated drop out of 10% a total of 980 patients will be included.

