7. METHODS

7.1 Study parameters/endpoints

7.1.1 Main study parameter

The primary endpoint is the number of ventilator-free days and alive at day 28, defined as the number of days from day 1 to day 28; the patient is alive and breathes without assistance of the mechanical ventilator, if the period of unassisted breathing lasted at least 24 consecutive hours.

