8.2 Secondary endpoints for safety

Since we compare two ventilation strategies that are currently used in standard care, additional risks are not expected. Furthermore, the study population consists of critically ill patients, with a high incidence of death or life-threatening events due to the severity of their illness (the hospital mortality in ventilated ICU patients is 21% ³⁴). Therefore, we propose to report the secondary endpoints of this trial, which incorporate ventilation specific complications, in a line listing two times per year to the METC to monitor safety of both treatment strategies. The METC will receive a line listing of the secondary endpoints incorporating ventilation specific ventilation complications (see below). These endpoints will be specified per study arm in the line listing without disclosing the specific arms.

Those ventilation specific complications include:

- ICU mortality
- Incidence of development of ARDS
- Incidence of severe hypoxemia
- Incidence of rescue therapy for severe hypoxemia and/or severe atelectasis:
 - Recruitment strategies
 - Prone positioning
 - Bronchoscopy for opening atelectasis

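### The 80% power in section 4.4 treats VFD-28 as lognormal with a CV of 0.70, which does not fit a 0 to 28 day endpoint with 5 expected days of ventilation

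*Protocol*

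**What the plan says.** Protocol section 4.4 sets out the calculation: "When the sample size in each is 445, an one–sided non–inferiority t–test (targeted at 0.05 significance level". The comparison is of means on the log scale, with 80% power against a 10% margin. The spread enters as follows: "anticipating on a coefficient of a variation of 0.70". The CV is credited to a national ICU registry and is applied to VFD-28. It is the only variance input.

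The same section explains the margin through ventilation time, "calculated over the expected mean duration of mechanical ventilation of 5 days". It gives no expected mean of VFD-28, no expected share of patients at zero and no rule for taking the log of a zero.

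Section 7.1.1 defines the endpoint as "the number of days from day 1 to day 28" on which the patient is alive and breathing unassisted, so it runs from 0 to 28. Section 8.2 notes that "the hospital mortality in ventilated ICU patients is 21" per cent. Section 9.2 plans a nonparametric confidence interval for the difference in medians.

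**The concern.** A lognormal variable is strictly positive and has no upper limit. VFD-28 has a hard ceiling at 28 days, lies close to that ceiling for a patient who is off the ventilator after 5 days, and can be zero. A bounded variable with a high mean has little room to vary, so a CV of 0.70 looks too large for it unless many patients sit at the bottom of the scale. If they do, the log transform on which the calculation rests breaks down.

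What is at stake is the power statement. Readers will judge the adequacy of the trial, and how to read a failure to show non-inferiority, against 80%.

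**Working it through.** **Inputs.** From 4.4: 445 per arm, one-sided 0.05, margin 10%, CV 0.70, mean ventilation time 5 days. From 7.1.1: range 0 to 28. From 8.2: hospital mortality 21%, used below as an assumed share of zeros.

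**1. The protocol's figure.** For a lognormal variable, log SD = sqrt(ln(1 + CV²)) = sqrt(ln 1.49) = 0.631. The margin as a ratio of 0.90 is −ln 0.90 = 0.105. A two-sample t-test with no true difference and one-sided 0.05 needs 445 per arm; noncentral t power at 445 is 80.0%. The figure reproduces exactly. Without the conversion (raw means, CV 0.70, margin 10% of the mean) about 606 per arm would be needed, so 445 does depend on the lognormal model.

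**2. How large can the CV be?** For any variable on 0 to 28 with mean m, the SD is at most sqrt(m(28 − m)), so CV ≤ sqrt((28 − m)/m). This needs no distributional assumption.
- m = 28 − 5 = 23 (everyone survives and stays off the ventilator): sqrt(5/23) = 0.466.
- CV = 0.70 requires m ≤ 28/(1 + 0.49) = 18.8.
- m = 18.2 (21% zeros: 0.79 × 23): ceiling 0.735.

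On 1 to 28, with no zeros at all, a CV of 0.70 is still attainable up to a mean of about 18.4, but at that limit only with patients heaped at 1 and at 28.

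**3. Does the sizing model respect the ceiling?** A lognormal with CV 0.70 places 26.5% of patients above 28 days if its mean is 23, and 15.9% if its mean is 18.2.

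**4. What does VFD-28 look like with zeros?** Assumed model: a share q scores 0; the others score 28 − D, with D lognormal, mean 5 days, CV of D from 0.7 to 1.5. Power is at 445 per arm, one-sided 0.05. The raw-mean margin is 10% of the mean; the log(x+1) margin is kept at −ln 0.90.

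| Zeros (q) | CV of VFD-28 | Power, raw means | SD of log(x+1) | Power, log(x+1) |
|---|---|---|---|---|
| 15% | 0.45 to 0.49 | 95 to 92% | 1.15 to 1.20 | 39 to 37% |
| 21% | 0.54 to 0.58 | 86 to 82% | 1.30 to 1.35 | 33 to 32% |
| 25% | 0.60 to 0.64 | 80 to 76% | 1.38 to 1.42 | 31 to 30% |
| 30% | 0.68 to 0.71 | 71 to 67% | 1.46 to 1.49 | 29 to 28% |

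A CV of 0.70 is reached at about 30% zeros. There log(VFD-28) is undefined for those patients, and with log(x+1) the SD is about 1.5, not 0.631.

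**5. Other reference cases.** Raw means with CV exactly 0.70: power 69% at 445 per arm. Protocol formula with the CV at its ceiling of 0.466 (mean 23): 219 per arm would suffice, and 445 gives 97%.

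**The case against.** The strongest reply is that 0.70 is not impossible. Section 4.4 never states a mean VFD-28 of 23; the 5 days is a ventilation time, used there to translate the margin into hours. Section 7.1.1 requires the patient to be alive, and at 21% zeros the ceiling is 0.735, so 0.70 is within reach. A strictly positive distribution with many very low counts, for instance from deaths soon after extubation, could reach it too. This stands: a reader might infer that VFD-28 can never have this CV, and the protocol does not support that.

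It does not rescue the 80%. The distributions on 0 to 28 that reach 0.70 have a large group at or near zero and the rest near the ceiling. The step from 0.70 to 0.631 is valid for a lognormal, which has neither feature.

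It is also fair that the alternative powers rest on assumed distributions, that neither the raw-mean nor the log(x+1) test is planned in the protocol, and that none of the figures is the power of the analysis in 9.2. They show how far the answer moves, not what it is.

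**Conclusion.** The inputs in 4.4 do not fit together. With few zeros, a 5-day mean ventilation time caps the CV at 0.466. With enough zeros to allow 0.70, the log transform and the conversion to a log SD of 0.631 do not apply. Either way, the stated 80% is not a supported property of 445 per arm.

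The bounds (0.466, 18.8 days, 0.735) follow from the 0 to 28 range and the means shown. The powers do not: they assume the mixture in the working, zeros equal to hospital mortality in the 21% case, and one-sided 0.05. They run from about 69% (raw means, CV 0.70), through 82 to 86% (raw means, 21% zeros) and from 95% to about 70% as zeros go from 15% to 30%, down to 32 to 33% (log(x+1), 21% zeros).

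Three stronger readings are tempting and unsupported. One is that the trial is underpowered: several cases exceed 80%, so the direction is open. Another is that 445 is a calculation slip: it is exact for its inputs. The third is that 0.70 is really the CV of ventilation duration: this is plausible, but the protocol does not say.

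**What to change.** In 4.4:
- state whether the 0.70 describes VFD-28 or ventilation duration;
- give the expected mean, SD and share of zeros of VFD-28, under the definition in 7.1.1 and from the same registry;
- drop the lognormal conversion;
- restate the power that 445 per arm gives for the 10% margin under the analysis planned in 9.2, for example by simulation from the registry distribution.

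The cost is one recalculation and a rewording of 4.4, with the chance that the stated power becomes less favourable. The request is to restate the figure, not to change enrolment.

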9.2 Primary study parameter

The primary outcome is the number of ventilator-free days and alive at day 28 after ICU admission. The null hypothesis entails that ventilation with the 'restricted PEEP'-arm is inferior by a margin of 10% to ventilation with the 'liberal PEEP'-arm. If the 95% CI upper bound for inferiority of the 'restricted PEEP'-arm is < 10%, the null hypothesis of inferiority is rejected. If the non-inferiority criterion is satisfied, then a secondary analysis of the primary endpoint for superiority will be tested. We will use an appropriate nonparametric analysis method to evaluate the confidence interval for the difference between the two medians of the ventilator-free days from both PEEP arms. Additionally, time to freedom from mechanical ventilation is expressed with Kaplan-Meier curves. Differences between both PEEP arms will be analyzed using the log-rank test.

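### Section 4.4 sets the non-inferiority margin at 10% of VFD-28 but explains it as 12 hours, which is 10% of ventilation duration; these are different margins.

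*Protocol*

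**What the plan says.** The sample size paragraph (Protocol 4.4) describes a one-sided 5% t-test on log-transformed data. Its null hypothesis is that VFD-28 under restricted PEEP is inferior "by a margin of 10% anticipating on a coefficient of a variation of 0.70". With 445 per arm the stated power is 80%. The 10% is motivated as the "maximal acceptable reduction of the ventilator–free period for non–inferiority".

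The next sentence translates it: "Clinically this margin means that an increase of > 10% in the" duration of mechanical ventilation lowers VFD-28 "with > 12 hours (calculated over the expected mean duration of mechanical ventilation of 5 days"), "which will be considered inferior".

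Section 7.1.1 counts the endpoint over four weeks: "defined as the number of days from day 1 to day 28". Section 9.2 places the test on this endpoint, with a null hypothesis that restricted PEEP "is inferior by a margin of 10% to ventilation with the" liberal arm, and plans a "confidence interval for the difference between the two medians of the ventilator-free days". It gives no value in days or hours. The protocol states no expected mean or median VFD-28.

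**The concern.** Section 4.4 attaches the same 10% to two quantities. The hypothesis and its motivation take 10% of the ventilator-free period, while the explanatory sentence takes 10% of the ventilated period. In a 28-day window with about 5 ventilated days, the first quantity is much larger than the second.

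In a non-inferiority trial the margin fixes what a positive result means. A reader of 4.4, including the ethics committee, would take success to show that at most about 12 hours are lost. The test in 9.2 may exclude only a loss several times larger. A true loss of 24 hours would be inferior under the 12-hour sentence, yet inside a 10% VFD-28 margin in every scenario worked through here. The 12-hour sentence is also the only quantified clinical justification of the margin.

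**Working it through.** **Inputs from the protocol.** Section 4.4: margin 10%, CV 0.70, one-sided 5%, power 80%, 445 per arm, mean ventilation 5 days. Section 7.1.1: 28-day window. Section 8.2: hospital mortality 21%, used below only as an assumed share of patients scoring zero.

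**1. The plan's own figure.** Log-scale SD = √ln(1 + 0.70²) = √ln 1.49 = 0.6315. Margin = |ln 0.90| = 0.1054. Then n per arm ≈ 2 × [(1.645 + 0.842) × 0.6315 / 0.1054]², which gives 445 after rounding up. The t-test power at 445 is 80.0%, so the figure reproduces.

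**2. Which variable the 445 fits.** On the log scale, 0.90 for VFD-28 and 1/0.90 for duration have the same absolute value, so 445 fits both. The duration version is +11.1%, or 120 h × 0.111 = 13.3 h. The increase printed in 4.4, exactly +10% (ln 1.10 = 0.0953), would need 543 per arm and has 73% power at 445.

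**3. Where 12 hours comes from.** 10% × 5 days × 24 h = 12 h = 0.5 day. For 0.5 day to be 10% of VFD-28, mean VFD-28 must be 0.5 / 0.10 = 5.0 days.

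**4. What 10% of VFD-28 is.** Assume 5 ventilated days, hence 23 free days, in patients with a non-zero score, and a share z scoring zero. Mean VFD-28 = (1 − z) × 23. The last column expresses the margin against 5 ventilated days.

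| z | Mean VFD-28 | 10% of it | Multiple of 12 h | As % of 5 days |
|---|---|---|---|---|
| 0 | 23.0 d | 55.2 h | 4.6 | 46% |
| 0.21 | 18.17 d | 43.6 h | 3.6 | 36% |
| 0.40 | 13.8 d | 33.1 h | 2.8 | 28% |

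**5. What the CV allows.** A variable confined to 0–28 with mean m has variance at most m(28 − m), so its CV is at most √((28 − m)/m). A CV of 0.70 therefore requires m ≤ 28/1.49 = 18.8 days, and 10% is then at most 1.88 days = 45 h (3.8 × 12 h). At m = 23 the largest possible CV is 0.47. The 55-hour row is therefore open only if the 0.70 describes something other than VFD-28.

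**6. On the median scale of 9.2.** Assuming log-normal duration (mean 5 days, CV 0.70) plus the same zero shares, the median VFD-28 is 23.9, 22.9 and 20.5 days, and 10% is 57, 55 and 49 hours.

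**7. Power at 445 per arm if 12 hours of VFD-28 is the limit.**

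- Raw-scale t-test, margin 0.5 day, SD 3.5 days in non-zero patients (0.70 × 5, taking the CV as that of duration). For z = 0, SD = 3.5 and power is 69%. For z = 0.21, SD = √(0.79 × 12.25 + 0.79 × 0.21 × 529) = 9.87 and power is 19%.
- The log-scale formula of 4.4, with CV 0.70 applied to VFD-28 (this formula cannot take zeros). Twelve hours is 2.2%, 2.75% and 3.6% of means of 23, 18.17 and 13.8 days, and power is 13%, 16% and 22%.

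All of these are below 80%.

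**The case against.** The strongest reply is that the operative margin is clear. The null hypothesis, the alternative and the stated motivation in 4.4 all name the ventilator-free period, and 9.2 tests the same outcome. Only one explanatory sentence speaks of duration. The match between 445 and a duration ratio of 1/0.90 is log symmetry: it yields 11.1% and 13.3 hours, neither of which is printed. On this view the design is sound and one sentence needs correcting.

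Most of this stands as a reading of intent, and it makes 10% of VFD-28 the likelier margin. It does not remove the contradiction. The sentence is offered as what the margin means and says what will count as inferior, so it is more than an illustration. A CV of 0.70 also rules out a mean VFD-28 above 18.8 days, so it is fair to ask which variable it describes.

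A second reply is that the sizes are soft. That is right. The 55-hour figure assumes no zeros and fails if the CV is that of VFD-28. In the same two-part model, a VFD-28 CV of 0.70 corresponds to about 31% zeros, a mean near 15.8 days and a margin near 38 hours (3.2 times 12). The powers for a 12-hour limit run from 13% to 69% depending on scale and zeros, so no single value should be relied on. In every variant the margin exceeds 12 hours several times over and the power stays below 80%.

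An analysis plan not seen here may add detail, but it cannot make both statements in 4.4 true.

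**Conclusion.** The concern holds, and the text must be corrected. Section 4.4 gives two incompatible margins under one label, and nothing in the protocol reconciles them. That conclusion needs no assumption beyond the observation that mean VFD-28 is not 5 days, which a 5-day mean ventilation time in a 28-day window makes implausible.

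The size of the gap is conditional, with moderate confidence. The margin tested is about 33 to 55 hours on the mean scale for 40% to 0% zeros with 5 ventilated days in the rest, and at most 45 hours if the CV of 0.70 belongs to VFD-28. The 445 per arm is arithmetically correct for a 10% log-scale margin. The stated 80% power does not carry over to a 12-hour limit on VFD-28.

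**What to change.** 1. The sponsor confirms whether the CV of 0.70 and the 445 per arm refer to VFD-28 or to ventilation duration.
2. Sections 4.4 and 9.2 state one margin on one scale for VFD-28, with the assumed control-arm value and the resulting loss in days.
3. The 12-hour sentence is removed or corrected, the margin actually tested is justified clinically, and the non-inferiority conclusion is limited to that margin.
4. If 12 hours is the intended limit, power is restated for it on VFD-28, with the assumed mean, SD and zero share.

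The cost is a text amendment, plausibly substantial and then notifiable to the ethics committee under section 11.3, and a margin that looks less favourable. Keeping 10% of VFD-28 with the calculation as stated needs no extra patients. Keeping 12 hours means 445 per arm falls short, by an amount that depends on the variable confirmed. As an indication, the raw-scale case with 21% zeros gives 2 × [(1.645 + 0.842) × 9.87 / 0.5]², about 4,800 per arm. That is far beyond a trial of 980, so correcting the sentence is the realistic course.
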